3.1 Design Summary

3.1.1 Study Design Schematic

3.1.2 Duration of Study Participation

Duration of Study participation per Subject is as follows:

- Screening: 45 days prior to and including Day 0 (day of surgery)

- Treatment Duration:
 - Customizable arm: 5 (+ 2) days
 - SOC arm: 2 (\pm 1) days
- Active Study Phase (after Randomization): Day 0 through 30 (\pm 4) days

The maximum participation duration per Subject is 80 days.

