5.6.1 Customizable with ActiV.A.C. Therapy Unit

Subjects randomized to the Customizable arm will receive therapy for 5 (+ 2) days.

Prior to dressing application, a topical skin adhesive (ie Mastisol, benzoin, Cavilon™) will be applied to the area around the closed incision, unless the Subject has a known allergy. The skin adhesive must not come in contact with the closed incision and will be applied after the Customizable foam is in place.

Customizable will be altered to cover the entirety of the incision and the tubing will be attached in close proximity to the center of the dressing. JP drains must not be covered by the dressing. An ActiV.A.C. Therapy Unit will then be connected to Customizable in the operating room and activated immediately.

After powering on the ActiV.A.C. Therapy Unit to deliver 125 mm/Hg of continuous negative pressure to the closed incision, the Investigator will ensure that Customizable is maintaining a seal.

The time of Customizable placement and the ActiV.A.C. Therapy Unit settings must be documented.

Customizable is intended to remain in place for the duration of therapy (at least 5 days) without requiring replacement. However, if Customizable develops a leak and all attempts to mitigate are unsuccessful, the dressing may be replaced to ensure continuity of negative pressure therapy. There is a two dressing replacement limit after the first Customizable is applied. If two replacements are attempted and negative pressure cannot be maintained, therapy will be discontinued and the subject will be treated as clinically appropriate. Customizable replacement will be documented.

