7.2 Premature Discontinuation of Subject

Subjects will be discontinued from the study if their randomly assigned treatment is ended prematurely, or if Customizable cannot maintain a seal even after replacing the dressing twice (see Section 5.6.1).

Subjects may withdraw from participation in the study at any time at their own request, or they may be withdrawn at any time at the discretion of the Investigator for safety, behavioral, or administrative reasons. If a Subject does not return for a scheduled visit, every effort should be made to contact the Subject, per the site's local protocol.

In any circumstance, every effort should be made to document Subject outcome. The Investigator should inquire about the reason for withdrawal, request that the Subject return for a final visit, if applicable, and follow-up with the Subject regarding any unresolved AEs. Any related SAEs occurring within 14 days following Subject discontinuation must be reported to KCI, and any applicable regulatory agencies and must be followed until stabilization or resolution.

If the Subject withdraws from the study, and also withdraws consent for disclosure of future information, no further study evaluations will be performed, and no additional data will be collected. The Investigator may retain and continue to use any data collected before such withdrawal of informed consent.

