9.7 Follow-Up Period for Ongoing AEs

Treatment-related AEs and SAEs which are ongoing at the final study visit, or treatment-related AEs that occur within 30 days of the final study visit, will be followed until resolution or stabilization. All other AEs will be closed at the time the Subject completes participation in the study.

10 Statistical Plan

The primary objective of the study is to compare surgical incision-related clinical outcomes in Subjects undergoing abdominal surgery for incisional hernia repair and/or functional panniculectomy when managed with Customizable as compared to SOC surgical incision dressing.

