8.1 Adverse Events

All treatment emergent adverse events will be coded using MedDRA coding dictionary (Version 20.0) and analyzed. An adverse event will be considered as treatment emergent (TEAE) if the onset is any time on or after the initial study surgery, panniculectomy or incisional hernia repair, through any time post surgery.

Number and percentage of treated subjects experiencing any TEAE will be summarized by system organ class and preferred term. Summary tables will be provided of incidences for all treatment emergent adverse events, treatment-related adverse events, adverse events by maximum severity, serious adverse events, serious adverse events related to study product and adverse events that led to study discontinuation. In any given category (e.g., system organ class or preferred term) a subject will be counted only once. If a subject has the same adverse event on multiple occasions, only the one with maximum severity will be presented. The denominator for the calculation of percentages will be the number of subjects in the sub-arm of subjects being tabulated and not the number of events.

Listings providing all serious adverse events, discontinuations due to any adverse event, or deaths occurring during the course of the study will be presented by subject.

The following summary tables and listings will be presented by treatment group and overall:

- Incidence of all treatment emergent adverse events by system organ class and preferred term.
- Incidence of all serious treatment emergent adverse events by system organ class and preferred term.
- Incidence of treatment-related adverse events by system organ class and preferred term.
- Incidence of treatment-related serious adverse events by system organ class and preferred term.
- Incidence of all treatment emergent adverse events by system organ class, preferred term, and maximum severity.
- Listing of all serious treatment emergent adverse events.
- Listing of all treatment-related serious adverse events.
- Listing of discontinuations: Subjects who discontinued from study due to any treatment emergent adverse event.
- Listing of deaths: Subjects who died of any cause during study.

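### Subjects who leave the study early have no single stated safety-reporting period (Protocol 7.2 and 9.7 are unreconciled), and the SAP's AE tables would not show the shorter observation

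*Protocol*

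**What the plan says.** Protocol 7.2 makes an early end of treatment an exit from the study: "Subjects will be discontinued from the study if their randomly assigned treatment is ended prematurely". The same applies when the Customizable seal still fails after two replacements. After exit the stated duty is: "Any related SAEs occurring within 14 days following Subject discontinuation must be reported to KCI". Section 7.2 also asks for best efforts to record the outcome, a final visit where applicable, and follow-up of unresolved AEs, but attaches no day to these.

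Protocol 5.6.1 covers the same seal failure and says only that "therapy will be discontinued and the subject will be treated as clinically appropriate". It does not mention leaving the study.

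Protocol 9.7 deals with related events that are ongoing at the final study visit and adds that "treatment-related AEs that occur within 30 days of the final study visit, will be followed until resolution or stabilization". It continues: "All other AEs will be closed at the time the Subject completes participation in the study". Neither 7.2 nor 9.7 refers to the other. Section 6.10 lists the early withdrawal procedures, including AE reporting, without saying whether that visit is the final study visit. Section 9.6.1 gives AE collection a start but no end.

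Protocol 10.2.2 and SAP 5.3 keep every randomised subject in the Safety Population once application of the dressing has been attempted, however short the treatment. SAP 8.1 counts an event as treatment-emergent if "the onset is any time on or after the initial study surgery, panniculectomy or incisional hernia repair, through any time post surgery". Its percentages use subjects as the denominator, and it does not ask for time under observation.

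**The concern.** A subject who leaves early falls under two clauses with different clocks, different scope and no stated order of precedence. A related SAE 20 days after discontinuation is outside the 14 days of 7.2. It is inside the 30 days of 9.7 only if the early withdrawal visit starts that clock. A site that consults the section on discontinuation could reasonably apply 7.2 alone.

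The route into this group is not symmetric. Seal failure can occur only with Customizable. Planned device therapy is also longer than planned SOC dressing, so there is more time in which it can end early. Protocol 5.7.2.2 adds that Customizable should be discontinued if infection is suspected. Read with 7.2, that too could lead to study exit.

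At stake is the descriptive safety comparison. Subjects seen for a few days and subjects seen for a month would each count as one in the denominator, and a reader of the AE tables could not tell them apart.

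**Working it through.** **Inputs.** Device therapy: "Subjects randomized to the Customizable arm will receive therapy for 5 (+ 2) days" (Protocol 5.6.1), so a premature stop falls on about Day 0 to 4; removal on Day 5 completes therapy. SOC dressing: 2 (±1) days (5.6.2), so a premature stop is possible only before about Day 1. Planned follow-up: "Active Study Phase (after Randomization): Day 0 through 30" with ±4 days (3.1.2), so Visit 9 falls on Day 26 to 34. Windows: 14 days after discontinuation (7.2) and 30 days after the final study visit (9.7).

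**Plan's own figure.** Maximum participation = 45 screening days + Day 0 + 34 days = 45 + 1 + 34 = 80 days, as stated in 3.1.2. The day count is therefore read as the protocol intends.

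**Formulas.** End of the 7.2 window = stop day + 14. Shortfall = target day − (stop day + 14). End of the 9.7 window = final-visit day + 30, assuming for early stoppers that the early withdrawal visit is on the stop day and counts as the final visit.

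| Stop day | 7.2 ends | Short of Day 26 | Short of Day 30 | Short of Day 34 | 9.7 would end |
|---|---|---|---|---|---|
| 0 | 14 | 12 | 16 | 20 | 30 |
| 1 | 15 | 11 | 15 | 19 | 31 |
| 2 | 16 | 10 | 14 | 18 | 32 |
| 3 | 17 | 9 | 13 | 17 | 33 |
| 4 | 18 | 8 | 12 | 16 | 34 |

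More generally, the 7.2 window ends before Day 26 for any exit before Day 12 (26 − 14), before Day 30 for any exit before Day 16, and before Day 34 for any exit before Day 20.

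**Completers under 9.7.** 26 + 30 = 56, 30 + 30 = 60 and 34 + 30 = 64, so treatment-related events are covered to Day 56 to 64.

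**By type of event after an early exit.**
- Related SAEs: 14 days under 7.2, or 30 days under 9.7 if the early withdrawal visit counts.
- Related non-serious AEs: no window in 7.2; 30 days under 9.7 on the same condition.
- New unrelated SAEs and new unrelated non-serious AEs: no window in either section. A completer is still assessed for these up to Visit 9.

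**The case against.** The strongest reply is that the two clauses are not rival values of one rule. Section 7.2 sets a minimum for reporting and following related SAEs after discontinuation, while 9.7 says which events are followed to resolution. Nothing says that 7.2 displaces 9.7. If the early withdrawal visit is the final study visit, 9.7 gives everyone 30 days after their last visit, and the gap before Day 30 closes for treatment-related events. Section 9.6.2 also requires SAEs to be reported within 24 hours of the site learning of them and states no end date. Section 7.2 asks for every effort to establish the outcome.

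Much of this stands. The Day 14 to 18 limit applies only at a site that works from 7.2 alone. Setting it against Day 56 to 64 for completers mixes two rules; under 9.7 alone the contrast is Day 30 to 34 against Day 56 to 64. What remains is that the text does not settle which reading applies, and neither section sets a window for new unrelated events.

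A reader might infer that the SAE comparison is biased in favour of the device. The documents do not support that. They give no count of seal failures, early stops or late SAEs. The general trigger in 7.2 applies to both arms, and SAP 8 makes the safety summaries descriptive. Nor can the treated subjects outside the FAS at the interim review (SAP 10) be used to size the group: early stoppers with an SSC remain in the FAS, and others can be excluded for eligibility or a missing Day 30 visit.

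**Conclusion.** The point holds as an unreconciled set of safety-reporting rules combined with a table design that would hide the result. For a Customizable stop on Day 0 to 4, required related-SAE reporting ends at Day 14 to 18 if 7.2 is applied alone. That is 8 to 12 days before the earliest Visit 9 and 12 to 16 days before Day 30. If 9.7 runs from an early withdrawal visit on the stop day, treatment-related events are covered to Day 30 to 34. On either reading, new unrelated events have no stated window after exit.

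Shorter observation may fall more on Customizable, because of the seal-failure rule and the longer planned therapy. How many subjects are affected, and whether any comparison is distorted, cannot be known from the documents. This is an inexpensive improvement worth making, not a demonstrated bias.

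**What to change.** **Protocol.** Reconcile 5.6.1, 7.2, 9.6.1 and 9.7 so that one stated safety-reporting period applies to all treated subjects and is no shorter for those who discontinue than for completers. State whether the 6.10 visit is the final study visit. Sections 5.6.1 and 7.2 must also agree on whether seal failure ends therapy only or study participation as well; no view is taken here on which.

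**SAP 8.1.** Tabulate AEs over a common period from surgery, through Day 34, which SAP 2 and 7.1 already use for clinical outcomes. List later events separately. Report days of observation by arm.

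**Cost.** One follow-up contact for each early-stopped subject, only where still feasible: SAP 5.2 records that enrolment has ended, so new protocol wording cannot recover data that were not collected. The SAP change is a small addition to the AE tables and can still be made for the study report.

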7.2.1 By Investigator

The Investigator may choose to discontinue the Subject from study with or without his/her consent for any of the following:

- AEs;
- Noncompliance; or
- Any reason that may, in the opinion of the Investigator, affect negatively the safety or well-being of the Subject.

If for any reason the Subject is withdrawn from the study, the Investigator will inform the Subject and KCI accordingly.

8 Risks Associated with Participation in the Study

Participation in this study presents low risks to Subjects. Risks associated with Customizable and the ActiV.A.C. Therapy Unit are generalized and are listed in Table 5 (Section 8.1).

8.1 Potential Risks Associated with Customizable and ActiV.A.C.

All risks known (based on prior relevant experience) or anticipated on reasonable grounds are listed. This table, and if needed this document, will be updated in the presence of new information of relevance to the safety of the Subject or the conduct of the study.

Table 5. Risks Associated with Customizable and ActiV.A.C.

Risks	Disorders/Conditions
Skin and Subcutaneous Tissue	
• Local cutaneous reaction (i.e. redness, rash, significant pruritis, urticaria)• Allergic reaction• Maceration• Minor soft tissue damage• Epidermal (skin) stripping• Minor bleeding• Pain• Contusion (bruising)
Other	
• Bleeding complications (associated with the surgical procedure, concomitant therapies and co-morbidities)• First degree burn (if device gets warm)• Exposure related infection• Localized infection• Physical discomfort• Minor desiccation (due to dressing leak)• Moderate soft tissue damage (i.e. due to trip hazard, tubing entanglement)• Deterioration of the wound (due to lack of visibility of incision site through dressing)

9 Safety and Adverse Events

9.1 Definition

9.1.1 Adverse Event (AE)

Any untoward medical occurrence, unintended disease or injury, or untoward clinical signs (including clinically significant abnormal laboratory findings) in Subjects, whether or not related to the study product.

This definition includes events:

- Related to the study product or the comparator,
- Related to the study procedures involved,
- Resulting from user error or from intentional misuse of the study product.

9.1.2 Serious Adverse Event (SAE)

An adverse event is considered serious if it results in any of the following outcomes:

- Death;
- Life-threatening adverse experience;

[figure not shown]
- Inpatient hospitalization or prolongation of existing hospitalization;
- Persistent or significant incapacity or substantial disruption of the ability to conduct normal life functions; or
- Congenital anomaly/birth defect.

Important medical events that may not result in death, be life threatening, or require hospitalization may be considered a serious adverse experience when, based upon medical judgment, they may jeopardize the patient or subject and may require medical or surgical intervention to prevent one of the outcomes listed in this definition (FDA, 21 CFR 312.32; ICH E2A and ICH E6).

9.1.2.1 Unanticipated Adverse Device Effect (UADE)

An UADE is any **serious adverse event** on health or safety or any life-threatening problem or death caused by, or associated with, a device, if that effect, problem, or death was not previously identified in nature, severity, or degree of incidence in the investigational plan or application (including a supplementary plan or application), or any other unanticipated serious problem associated with a device that relates to the rights, safety, or welfare of subjects. (21 CFR 812.3)

9.2 Classification

9.3 Causality

The Investigator will assess the causality of the AE as:

- Related to the study product: any adverse event for which there is a reasonable possibility that the study product caused the adverse event.
- Not Related to the study product: when is determined that there is no relationship between the adverse event and the use of the study product.

9.4 Severity

All AEs will be assessed for severity by Grade based upon the following definitions:

- **Grade 1: Mild;** Awareness of signs or symptoms, but easily tolerated and are of minor irritant type to the Subject, causing no loss of time from normal activities. Symptoms do not require therapy or a medical evaluation; signs and symptoms are transient.
- **Grade 2: Moderate;** Events introduce a low level of inconvenience or concern to the Subject and may interfere with daily activities, but are usually improved by simple therapeutic measures; moderate experiences may cause some interference with functioning; minimal, local or noninvasive intervention indicated.
- **Grade 3: Severe;** Events interrupt the Subject's normal daily activities and generally require systemic drug therapy or other treatment; they are usually incapacitating.

9.5 Expectedness

All SAEs will be assessed for expectedness based on the following definitions:

- **Expected, Anticipated:** the effect, problem, or death had been previously identified in nature, severity, or degree of incidence in the study or product documentation.
- **Unexpected, Unanticipated:** if that effect, problem, or death was not previously identified in nature, severity, or degree of incidence in the study or product documentation.

9.6 AE Reporting Procedures

The Investigator is responsible for monitoring the safety of all Subjects enrolled in the study, and reporting adverse events as described in this protocol.

9.6.1 AE Collection/Reporting Period

The AE collection/reporting period will begin after the Subject has completed any study related procedures after informed consent. Exceptions to this are clinically significant laboratory findings or diagnostic tests performed as part of screening. These will be recorded on the Medical History CRF and not as adverse events.

Study Subjects should be instructed to report any AE that they experience to the Investigator. Investigators should assess for AEs at each visit. All AEs, regardless of perceived relationship to study product, will be reported and recorded on the appropriate CRFs in a timely manner. In addition, **clinically significant** changes in physical examination findings, worsening of a medical condition in the medical history and abnormal test findings should also be recorded as AEs.

The AE description will include the nature of the event (AE term), the start date, the end date, the severity of each sign or symptom, the seriousness of the event or experience, causality, the course of action taken, and the outcome of the event.

9.6.2 SAE Reporting to KCI

Serious Adverse Events (SAE) will be reported via the KCI SAE Report Form within 24 hours of learning of the event. This form should be completed by the Investigator, or designee, and faxed or emailed to KCI. Initial notification of the event may occur via telephone call to a KCI study contact, but must always be followed by written notification using the SAE Report Form by the close of the next business day. The KCI SAE fax line is available for SAE reporting 24 hours per day and is monitored during normal business hours. The SAE fax number and email address can be found in the Study Reference Binder.

9.6.2.1 UADE Reporting to KCI

UADEs must be reported by the Investigator to the Sponsor and the reviewing Institutional Review Board (IRB) per their reporting requirements (see SAE Reporting, Section 9.6.2). The Sponsor (KCI) will then immediately conduct an evaluation of a UADE and report the results of the evaluation to the FDA and participating Investigators within 10 working days after the Sponsor first receives notice of the event. (21 CFR 812.46(b), 812.150(b) (1)).

If KCI determines that the event presents an unreasonable risk to the study Subjects, it will terminate all clinical studies or parts of studies presenting risk as soon as possible. In this case,

termination will occur \leq 5 working days after KCI makes the determination and \leq 15 working days after KCI first received notice of the event.

9.7 Follow-Up Period for Ongoing AEs

Treatment-related AEs and SAEs which are ongoing at the final study visit, or treatment-related AEs that occur within 30 days of the final study visit, will be followed until resolution or stabilization. All other AEs will be closed at the time the Subject completes participation in the study.

10 Statistical Plan

The primary objective of the study is to compare surgical incision-related clinical outcomes in Subjects undergoing abdominal surgery for incisional hernia repair and/or functional panniculectomy when managed with Customizable as compared to SOC surgical incision dressing.

10.1 Sample Size Determination

The primary endpoint of this study is the incidence of SSC as defined in Section 5.7.1. The incidence rates of SSC will be compared between the treatment groups using Fisher's exact test.

A review of relevant literature shows that both Neaman and Greco reported surgical site complication rates for obese patients of 53.4% and 43.0%, which included rates of dehiscence and SSI of 12.3-15.4% and 16.9-26.0%, respectively.^{53;54} Vargo and Condé-Green reported large treatment effects of NPWT over closed incision versus the standard of care in complex abdominal wall reconstruction of 85% and 65%, respectively.^{55;56} Considering these references and the design of the current trial, a 35% rate of SSC is projected for the SOC arm, which is consistent with the clinical experience of the Investigators. Based on the primary endpoint of incidence rate of SSC, Fisher's exact test with a two-sided significance level $\alpha = 0.05$ will have approximately 80% power to detect the difference between an incidence rate of 35% in the SOC arm and an incidence rate of 8.75% in the Customizable arm (a 75% reduction) when the sample size in each arm is 44. To account for possible Subject replacement, the sample will be increased by up to 15% for a maximum total of 102 Subjects (51 in each treatment arm).

Due to the wide ranges of SSC incidence rate for the SOC group found in published literature, and no data from use of Customizable dressing for this study population, one planned interim data review will be performed to allow for an adjustment of the sample size. The total number of

treatment emergent AEs and SAEs (Section 10.6) and the SSC incidence rates (Section 10.5.1) will be calculated for each treatment group using the ITT population (Section 10.2.2). Since the purpose of the interim data review is not for any statistical comparison of effectiveness, no adjustment for multiplicity will be made in the final analysis.

Estimates in Table 8 were prepared to examine the SSC rates in the interim data review for sample size justification purposes only. The observed SSC incidence rates may be used to justify increasing the sample size up to 500 Subjects if the original sample size assumptions are incorrect.

Table 8 contains the estimated total sample size based on possible SSC incidence rates using Fisher's exact test with a two-sided significance level $\alpha = 0.05$ and $\beta = .20$. If the observed rates fall between the values displayed in Table 8, the SOC rate will round to the lower rate (e.g., 33.8% will round to 32.5%) and the Customizable rate will round to the higher rate (e.g., 13.4% will round to 15.0%).

Following the interim data review, the sample size will not be adjusted if the observed rates of SSC within the ITT population do not belong to the pre-specified estimates in Table 8, and the sample size will remain at 102 Subjects. The sample size and power calculations were performed using SAS version 9.3.

Table 8: Total sample size estimate for the observed SSC incidence rates of the first 60 subjects in the ITT population.

SSC Incidence Rate	Standard of Care								
	40.0%	37.5%	35.0%	32.5%	30.0%	27.5%	25.0%	22.5%	20.0%
Customizable	20.0%	196	248	324	452				
	17.5%	152	184	234	418	424			
	15.0%	118	142	174	220	286	394		
	12.5%		112	134	162	202	264	360	
	10.0%			102	122	148	184	236	322
	7.5%					112	134	164	210
	5.0%							116	142
To account for possible Subject replacement, sample estimates were modified using the following calculation:									
Total Sample = (Estimated Sample - 60)*1.10 + 60									
Sample estimated as described in Section 10.1									

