10.3 Randomization

Subjects who meet all inclusion criteria and no exclusion criteria and who consent to participate in the study will be randomized in a 1:1 ratio to be treated with either Customizable or SOC surgical incision dressing. Due to the variances in complication rates between incision types, a stratified randomization will be used to ensure balance between the groups. The randomization will be stratified for each site and incision type of vertical/transverse and fleur-de-lis. Within each stratum, permuted blocks will be used to achieve equal numbers of Subjects assigned to Customizable or SOC surgical incision dressing. For each stratum, a randomization schedule will be generated to include Subject numbers and treatment assignments with the stratum of transverse/vertical incision starting with 1001 and the stratum of fleur-de-lis incision starting with 2001. Corresponding randomization envelopes will be prepared in sequential order by Subject number to provide randomization to each Investigator.

Randomization envelopes will be prepared corresponding to each row in the randomization schedule. Subject numbers will be printed and labeled clearly on the top of each envelope. Additionally, the envelopes will be color coded for incision type stratum, sealed, and organized by stratum and in ascending by Subject number

Once the Subject has been screened, deemed eligible, and provided informed consent, the next available sequentially numbered randomization envelope within the corresponding stratum according to incision type; a sealed Customizable box and ActiV.A.C. unit will be taken into the operating room with the Subject. Randomization will be conducted in the operating room after closure of the surgical incision and confirmation of intra-operative eligibility. The envelope will be opened prior to surgical incision dressing placement and the assigned treatment arm will be used. If Customizable is not selected, the sealed box and ActiV.A.C. unit will be returned to appropriate storage area.

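### Table 8 gives 418 subjects for SOC 32.5% / Customizable 17.5%, but the protocol's stated method gives 308

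*Protocol*

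**What the plan says.** Protocol section 10.1 (Sample Size Determination) plans one interim data review at about 60 subjects. The SSC rates seen there may be used to justify raising the total, to at most 500. Table 8 supplies the new total for each pair of rates. Its stated basis is Fisher's exact test at two-sided alpha 0.05 with beta 0.20, and the text adds: "The sample size and power calculations were performed using SAS version 9.3". The footnote applies a replacement allowance: "Total Sample = (Estimated Sample - 60)*1.10 + 60".

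Observed rates that lie between table values are moved to a cell by rule: "If the observed rates fall between the values displayed in Table 8, the SOC rate will round to the lower rate", and the Customizable rate rounds to the higher one. Section 10.3 sets 1:1 allocation.

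The SOC columns run from 40.0% down to 20.0% in steps of 2.5 points. The Customizable 17.5% row is printed as "17.5% 152 184 234 418 424", which gives 418 for SOC 32.5%.

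**The concern.** The row is irregular on its face. As the SOC rate falls towards a fixed Customizable rate, the required size should rise by growing steps. The printed row 152, 184, 234, 418, 424 has steps of 32, 50, 184 and 6: a very large jump, then almost none.

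Table 8 is the only conversion from interim rates to a new total that the protocol provides. Under the rounding rule, an SOC rate from 32.5% to just under 35% together with a Customizable rate above 15% and up to 17.5% goes to this cell. That SOC range lies just below the 35% assumed in the design. If the entry is too large, the plan would support randomising more subjects than its own power target needs, and this cell would be sized to a different power from all the others.

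**Working it through.** **Inputs.** Test, alpha, beta, the table and the inflation formula come from Protocol section 10.1; 1:1 allocation comes from section 10.3. The documents do not name the approximation used for Fisher power, nor how totals were rounded. I used the arcsine approximation with continuity correction (Walters) and rounded each inflated total up to an even number. Both choices are inferred, and are tested below against the plan's own figures.

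**Formula.** With p1 the SOC rate, p2 the Customizable rate and n per arm:

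power = Φ( √(2n) × [asin√(p1 − 1/(2n)) − asin√(p2 + 1/(2n))] − 1.96 )

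**Step 1: reproduce the base design.** Section 10.1 states about 80% power for 35% against "an incidence rate of 8.75% in the Customizable arm (a 75% reduction) when the sample size in each arm is 44". At n = 44: √88 = 9.381; the arcsine terms are 0.6211 and 0.3199; the product is 2.826; power is Φ(0.866) = 0.807. Exact enumeration of Fisher's test also gives 0.807. The 15% allowance gives 88 × 1.15 = 101.2, and the protocol states 102, which agrees with rounding up to an even total.

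**Step 2: reproduce Table 8.** For each cell, take the smallest n per arm with power of at least 0.80, double it, apply (N − 60) × 1.10 + 60, and round up to even. The 17.5% row, and the other cells in the SOC 32.5% column, give:

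| SOC | Customizable | Raw total | Inflated | Even total | Printed |
|---|---|---|---|---|---|
| 40.0% | 17.5% | 142 | 150.2 | 152 | 152 |
| 37.5% | 17.5% | 172 | 183.2 | 184 | 184 |
| 35.0% | 17.5% | 218 | 233.8 | 234 | 234 |
| **32.5%** | **17.5%** | **284** | **306.4** | **308** | **418** |
| 30.0% | 17.5% | 390 | 423.0 | 424 | 424 |
| 32.5% | 20.0% | 416 | 451.6 | 452 | 452 |
| 32.5% | 15.0% | 204 | 218.4 | 220 | 220 |
| 32.5% | 12.5% | 152 | 161.2 | 162 | 162 |
| 32.5% | 10.0% | 116 | 121.6 | 122 | 122 |

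Over the whole table, 32 of the 33 filled cells match exactly. The only mismatch is SOC 32.5% / Customizable 17.5%.

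**Step 3: the cell in detail.** At n = 141, approximate power is 0.799. At n = 142: √284 = 16.852; the arcsine terms are 0.6028 and 0.4362; the product is 2.808; power is 0.802. So n = 142 per arm and the raw total is 284. Then (284 − 60) × 1.10 + 60 = 306.4, which rounds to 308. The excess is 418 − 308 = 110, and 110 / 308 = 36%.

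Exact enumeration of Fisher power gives 0.798 at 140 per arm, 0.802 at 141 and 0.805 at 142. If the exact calculation had been used, 141 per arm gives 282, inflated 304.2, even total 306.

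**Step 4: look for a route to 418.** None of the alternatives tried for this cell gives it:

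- Normal approximation with continuity correction: 286, inflated 308.6.
- Normal approximation without correction: 260, inflated 280.0.
- Walters at 85%, 90% and 95% power: inflated 346.0, 401.0 and 491.2.

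**Step 5: what 418 implies.** Removing the allowance, (418 − 60) / 1.10 + 60 = 385.5, or 192 complete pairs. Exact power at 192 per arm for 32.5% against 17.5% is 0.912.

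**Step 6: regularity.** With 308 the row is 152, 184, 234, 308, 424, with steps of 32, 50, 74 and 116.

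**The case against.** The arithmetic is hard to dispute; the case on the other side is about consequence and wording.

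- **The cell was not used.** SAP section 10 reports interim SSC rates of 17.2% on Customizable and 3.1% on SOC, outside Table 8. SAP section 5.2 records that enrolment then stopped at 71 subjects. No subject was enrolled and no result changed because of this number. This stands.
- **An increase is permitted, not automatic.** Section 10.1 says the observed rates may be used to justify an increase. This stands: the entry could have justified 110 extra subjects, but would not have forced them.
- **The cell is rarely reached.** With 30 per arm at the review, only 10/30 on SOC with 5/30 on Customizable falls in it. The chance is about 1% under the design rates (35% and 8.75%), and about 3% if the true rates are 32.5% and 17.5%. This stands, and limits the practical risk.
- **The error raises power.** The harm is surplus enrolment, not an underpowered trial. The rounding rule also errs high by design: at 33.3% against 16.7%, a total of 308 already has about 0.88 power, and 418 about 0.96. This stands.
- **308 depends on an inferred approximation and rounding.** True, but 32 exact matches support both, and the exact calculation moves the answer only to 306.
- **The table was machine-read.** 308 and 418 differ in two digits, so one misread character does not explain the gap. The cells on either side, above and below all reproduce in position, so a shifted column does not explain it either. The printed page should still be checked.

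**Conclusion.** The point holds. The Table 8 entry for SOC 32.5% / Customizable 17.5% does not follow from the method the protocol states. It should be 308 and is printed as 418: 110 subjects (36%) too many, with power of about 0.91 at those rates where the table specifies 0.80. The error is confined to this one cell.

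The conclusion assumes the Walters approximation and rounding up to an even total, both supported by the 32 matching cells, and it assumes that the machine-read 418 is what the original page shows. Exact enumeration would give 306, which leaves the conclusion unchanged.

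The entry had no effect on this trial, because the interim rates fell outside the table. It matters because it is a pre-specified decision figure, and anyone who consults or reuses the table would be misled.

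**What to change.** Check the cell against the original protocol page and the SAS sample size output, then replace 418 with 308. If the output shows that exact enumeration was used for this cell alone, 306 would be the figure. No other cell needs changing.

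The cost is one number in the protocol, with no change to the design, the analysis or the data. Since enrolment has closed, an erratum would be enough, or a note in the clinical study report beside the interim data review plan and results, which SAP section 10 says may be included there.
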